15.2. Publications by Investigators

Pfizer supports the exercise of academic freedom and has no objection to publication by principal investigator of the results of the study based on information collected or generated by principal investigator, whether or not the results are favorable to the Pfizer product. However, to ensure against inadvertent disclosure of confidential information or unprotected inventions, the investigator will provide Pfizer an opportunity to review any proposed publication or other type of disclosure of the results of the study (collectively, "Publication") before it is submitted or otherwise disclosed.

The investigator will provide any publication to Pfizer at least 30 days before they are submitted for publication or otherwise disclosed. If any patent action is required to protect intellectual property rights, the investigator agrees to delay the disclosure for a period not to exceed an additional 60 days.

The investigator will, on request, remove any previously undisclosed confidential information before disclosure, except for any study- or Pfizer product-related information necessary to the appropriate scientific presentation or understanding of the study results.

If the study is part of a multicenter study, the investigator agrees that the first publication is to be a joint publication covering all study sites, and that any subsequent publications by the principal investigator will reference that primary publication.. However, if a joint manuscript has not been submitted for publication within 12 months of completion or termination of the study at all participating sites, the investigator is free to publish separately, subject to the other requirements of this section.

For all publications relating to the study, the institution will comply with recognized ethical standards concerning publications and authorship, including Section II - "Ethical

Considerations in the Conduct and Reporting of Research” of the Uniform Requirements for Manuscripts Submitted to Biomedical Journals, <http://www.icmje.org/index.html#authorship>, established by the International Committee of Medical Journal Editors.

Publication of study results is also provided for in the CSA between Pfizer and the institution. In this section entitled **Publications by Investigators**, the defined terms shall have the meanings given to them in the CSA.

If there is any conflict between the CSA and any Attachments to it, the terms of the CSA control. If there is any conflict between this protocol and the CSA, this protocol will control as to any issue regarding treatment of study subjects, and the CSA will control as to all other issues.

Appendix 1. Abbreviations

This is a list of abbreviations that may be used in the protocol.

Abbreviation	Term
AD	atopic dermatitis
AE	adverse event
ALT	alanine aminotransferase
AST	aspartate aminotransferase
ATP	adenosine triphosphate
AUC	area under the concentration-time curve
AUC _{inf}	area under the plasma concentration-time curve from time zero to infinity
AUC _{last}	area under the plasma concentration time curve from time zero extrapolated to the last quantifiable concentration
AUC _{tau}	area under the plasma concentration-time curve from time zero to 24 hours
BA	bioavailability
BCG	bacille calmette guérin
BP	blood pressure
BSA	body surface area
CDS	core data sheet
CL	clearance
C _{max}	maximum plasma concentration
CMV	cytomegalovirus
CRF	case report form
CSA	clinical study agreement
CsA	cyclosporine A
CSF	cerebrospinal fluid
CT	computed tomography
CTA	clinical trial application
CTCAE	common terminology criteria for adverse events
DAI	dosage and administration instructions
DDI	drug-drug interaction
DLQI	dermatology life quality index
DMC	data monitoring committee
DNA	deoxyribonucleic acid
DU	dispensable unit
EASI	eczema area and severity index
EBV	epstein barr virus
EC	ethics committee
ECG	electrocardiogram
EDMC	external data monitoring committee
EDP	exposure during pregnancy

Abbreviation	Term
EDTA	edetic acid (ethylenediaminetetraacetic acid)
EFD	embryo-fetal development
ELISA	enzyme-linked immunosorbent assay
EOT	end of treatment
EPO	erythropoietin
ET	early termination
EU	European Union
EudraCT	European Clinical Trials Database
FACS	fluorescence-activated cell sorting
FDA	Food and Drug Administration (United States)
FDAAA	Food and Drug Administration Amendments Act (United States)
FIH	first-in-human
FSH	follicle-stimulating hormone
GCP	good clinical practice
GM-CSF	granulocyte-macrophage colony-stimulating factor
HADS	hospital and anxiety depression scale
HBcAb	hepatitis B core antibody
HBsAb	hepatitis B surface antibody
HBsAg	hepatitis B surface antigen
HEENT	head, eyes, ears, nose and throat
HIV	human immunodeficiency virus
HRQL	health-related quality of life
hsCRP	high-sensitivity C-reactive protein
IB	investigator's brochure
ICH	International Conference on Harmonisation
ID	identification
IFN α	interferon alfa
IFN γ	interferon gamma
IGA	investigator's global assessment
IgE	immunoglobulin E
IL	interleukin
IND	investigational new drug application
INR	international normalized ratio
IOBU-SDMC	Internal Oncology Business Unit-Safety Data Monitoring Committee
IP-10	interferon gamma-induced protein 10
IRB	institutional review board
IRC	internal review committee
IRT	interactive response technology
IUD	intrauterine device
IVRS	interactive voice response system
IWR	interactive web response
JAK	janus kinase

090177e18dabc380\0.1\Draft\Versioned On:07-Feb-2018 09:59 (GMT)

Abbreviation	Term
LFT	liver function test
LLN	lower limit of normal
LPD	local product document
LSLV	last subject last visit
MAD	multiple ascending dose
MDCK/MDR1	Madin Darby canine kidney cell line/multidrug resistance 1 gene
mITT	modified intention-to-treat
MMRM	mixed-effect models repeated measures
MRI	magnetic resonance imaging
MTX	methotrexate
N/A	not applicable
NADPH	nicotinamide adenine dinucleotide phosphate
NK	non-killer cells
NOAEL	no observed adverse effect level
NRS	numerical rating scale
OBU	oncology business unit
PCD	primary completion date
PD	pharmacodynamic
PFS	pre-filled syringe
P-gp	P-glycoprotein
PK	pharmacokinetic
POC	proof-of-concept
POEM	patient Oriented Eczema Measure
POM	proof of mechanism
PPD	purified protein derivative
PRO	patient reported outcomes
CCI	
PT	prothrombin time
PtGA	patient global assessment
QD	once daily
QFT-G	QuantiFERON [®] -TB Gold
R _{ac}	accumulation ratio
RNA	ribonucleic acid
RRCK	ralph russ canine kidney cells
SAD	single ascending dose
SAE	serious adverse event
SAP	statistical analysis plan
SC	subcutaneous
SCL	supply chain lead
SCORAD	SCORing atopic dermatitis
SIB	suicidal ideation and behavior
SOC	system organ class
SOP	standard operating procedure

090177e18dabc380\0.1\Draft\Versioned On:07-Feb-2018 09:59 (GMT)

Abbreviation	Term
SPC	summary of product characteristics
SRSD	single reference safety document
STATs	signal transducers and activators of transcription
$t_{1/2}$	half life
TB	tuberculosis
TDAR	T cell-dependent antibody response
TEAE	treatment-emergent adverse event
T_H1	type 1 helper T cell
T_H2	type 2 helper T cell
T_{max}	the time after administration of a drug when the maximum plasma concentration is reached
TYK2	tyrosine kinase 2
ULN	upper limit of normal
US	United States
USPI	United States package insert
UVA	ultraviolet A light
UVB	ultraviolet B light
UVR	ultraviolet radiation
VAS	visual analogue scale
VZV	varicella zoster virus

Appendix 2. Diagnostic Criteria for Atopic Dermatitis

A subject is to have a clinical diagnosis of atopic dermatitis according to the criteria of Hanifin and Rajka.

Hanifin and Rajka's Diagnostic Criteria for Atopic Dermatitis

Major Criteria (must have at least three)

Pruritus

Typical morphology and distribution:

Adults: flexural lichenification or linearity

Children and infants: involvement of facial and extensor surfaces

Chronic or relapsing dermatitis

Personal or family history of atopy

Minor Criteria (must have at least three)

Xerosis

Ichthyosis/keratosis pilaris/palmer hyperlinearity

Immediate (type 1) skin test reactivity

Elevated serum IgE

Early age at onset

Tendency to skin infections (Staphylococcus aureus, herpes simplex)/impaired cellular immunity

Hand/foot dermatitis

Nipple eczema

Conjunctivitis

Dennie-Morgan fold

Keratoconus

Anterior subcapsular cataracts

Orbital darkening

Facial pallor/erythema

Pityriasis alba

Anterior neck folds

Itch when sweating

Intolerance to wool and lipid solvents

Perifollicular accentuation

Food intolerance

Course influenced by environmental/emotional factors

White demographic/delayed blanch

Appendix 3. Prohibited Concomitant Medications

CYP3A4, 5,7 Inhibitors

HIV antivirals:
-delavirdine (Rescriptor)
-indinavir (Crixivan)
-nelfinavir (Viracept)
-ritonavir (Kaletra, Norvir)
-saquinavir (Fortovase)
amiodarone (Cordarone, Pacerone)
cimetidine (Tagamet)
ciprofloxacin (Cipro)
clarithromycin (Biaxin, Prevpac)
diethyl-dithiocarbamate
diltiazem (Cardizem, Tiazac)
erythromycin
fluconazole (Diflucan)
fluvoxamine (Luvox)
gestodene (Femodene, Melodene, Minulette,
Mirelle, Triodene ED)
grapefruit juice and marmalade
itraconazole (Sporanox)
ketoconazole (Nizoral)
mifepristone (Mifeprex, RU486)
nefazodone (Serzone)
norfloxacin (Shibroxin, Noroxin)
Norflouxetine
Mibefradil
verapamil (Calan SR, Covera HS, Isoptin SR,
Tarka, Verelan)

CYP3A Inducers

efavirenz (Sustiva)
nevirapine (Viramune)
barbiturates
carbamazepine (Carbatrol, Tegretol)
modafinil (Provigil)
phenobarbital
Phenytoin (Dilantin, Phenytek)
rifampin (Rifadin, Rifamate, Rifater)
St. John's wort
troglitazone (Rezulin)
pioglitazone (Actos)
rifabutin (Mycobutin)

Appendix 4. Fitzpatrick Skin Type

Phototype	Sunburn and tanning history (defines the phototype)
I	Burns easily, never tans
II	Burns easily, tans minimally with difficulty
III	Burns moderately, tans moderately and uniformly
IV	Burns minimally, tans moderately and easily
V	Rarely burns, tans profusely
VI	Never burns, tans profusely

Appendix 5. Patient Global Assessment (PtGA)

Overall, how would you describe your Atopic Dermatitis right now?

Choose only ONE response.

- Severe
- Moderate
- Mild
- Almost Clear
- Clear

Appendix 6. Pruritus Severity and Frequency

Severity of Pruritus

Select the number that best describes your itching due to Atopic Dermatitis over the past 24 hours (check one number only).

										
0	1	2	3	4	5	6	7	8	9	10
No itching									Worst possible itching	

Frequency of Pruritus

Select the number that best describes frequency of itching due to Atopic Dermatitis over the past 24 hours (check one number only).

										
0	1	2	3	4	5	6	7	8	9	10
Never /No itching									Always/constant itching	

Appendix 7. Dermatology Life Quality Index (DLQI)

1.	Over the last week, how itchy, sore, painful or stinging has your skin been?	Very much A lot A little Not at all	   	
2.	Over the last week, how embarrassed or self conscious have you been because of your skin?	Very much A lot A little Not at all	   	
3.	Over the last week, how much has your skin interfered with you going shopping or looking after your home or garden?	Very much A lot A little Not at all	   	Not relevant 
4.	Over the last week, how much has your skin influenced the clothes you wear?	Very much A lot A little Not at all	   	Not relevant 
5.	Over the last week, how much has your skin affected any social or leisure activities?	Very much A lot A little Not at all	   	Not relevant 
6.	Over the last week, how much has your skin made it difficult for you to do any sport?	Very much A lot A little Not at all	   	Not relevant 
7.	Over the last week, has your skin prevented you from working or studying?	yes no	 	Not relevant 
	If "No", over the last week how much has your skin been a problem at work or studying?	A lot A little Not at all	  	
8.	Over the last week, how much has your skin created problems with your partner or any of your close friends or relatives?	Very much A lot A little Not at all	   	Not relevant 
9.	Over the last week, how much has your skin caused any sexual difficulties?	Very much A lot A little Not at all	   	Not relevant 
10.	Over the last week, how much of a problem has the treatment for your skin been, for example by making your home messy, or by taking up time?	Very much A lot A little Not at all	   	Not relevant 

090177e18dabc380\0.1\Draft\Versioned On:07-Feb-2018 09:59 (GMT)

Appendix 8. Patient-Oriented Eczema Measure (POEM)

Please circle one response for each of the seven questions below about your eczema.
Please leave blank any questions you feel unable to answer.

1. Over the last week, on how many days has your skin been itchy because of your eczema?

No days 1-2 days 3-4 days 5-6 days Every day

2. Over the last week, on how many nights has your sleep been disturbed because of your eczema?

No days 1-2 days 3-4 days 5-6 days Every day

3. Over the last week, on how many days has your skin been bleeding because of your eczema?

No days 1-2 days 3-4 days 5-6 days Every day

4. Over the last week, on how many days has your skin been weeping or oozing clear fluid because of your eczema?

No days 1-2 days 3-4 days 5-6 days Every day

5. Over the last week, on how many days has your skin been cracked because of your eczema?

No days 1-2 days 3-4 days 5-6 days Every day

6. Over the last week, on how many days has your skin been flaking off because of your eczema?

No days 1-2 days 3-4 days 5-6 days Every day

7. Over the last week, on how many days has your skin felt dry or rough because of your eczema?

No days 1-2 days 3-4 days 5-6 days Every day

Appendix 9. Hospital and Anxiety Depression Scale (HADS)

1. I feel tense or 'wound up'
 
 3 Most of the time  2 A lot of the time  1 From time to time, occasionally  0 Not at all
 
2. I still enjoy the things I used to enjoy
 
 0 Definitely as much  1 Not quite so much  2 Only a little  3 Hardly at all
 
3. I get a sort of frightened feeling as if something awful is about to happen
 
 3 Very definitely and quite badly  2 Yes but not too badly  1 A little, but it doesn't worry me  0 Not at all
 
4. I can laugh and see the funny side of things
 
 0 As much as I always could  1 Not quite so much now  2 Definitely not so much now  3 Not at all
	
5. Worrying thoughts go through my mind
 
 3 A great deal of the time  2 A lot of the time  1 Not too often  0 Very little
 
6. I feel cheerful
 
 3 Never  2 Not often  1 Sometimes  0 Most of the time
 
7. I can sit at ease and feel relaxed
 
 0 Definitely  1 Usually  2 Not often  3 Not at all
 
8. I feel as if I am slowed down
 
 3 Nearly all of the time  2 Very often  1 Sometimes  0 Not at all

--	--


9. I get a sort of frightened feeling like 'butterflies' in the stomach
 
 0 Not at all  1 Occasionally  2 Quite often  3 Very often
 
10. I have lost interest in my appearance
 
 3 Definitely  2 I don't take as much care as I should  1 I may not take quite as much care  0 I take just as much care as ever
 
11. I feel restless as if I have to be on the move
 
 3 Very much indeed  2 Quite a lot  1 Not very much  0 Not at all
	
12. I look forward with enjoyment to things
 
 0 As much as I ever did  1 Rather less than I used to  2 Definitely less than I used to  3 Hardly at all
 
13. I get sudden feelings of panic
 
 3 Very often indeed  2 Quite often  1 Not very often  0 Not at all
 
14. I can enjoy a good book or radio or television program
 
 0 Often  1 Sometimes  2 Not often  3 Very seldom

--	--

Appendix 11. Guidelines for Subject Safety Monitoring and Discontinuation

These guidelines for subject safety monitoring and discontinuation are to be applied to all subjects in study B7451006. Additional individual subject monitoring is at the discretion of the investigator and dependent on any perceived safety concerns. Unscheduled clinical labs may be obtained at any time during the study to assess such concerns, and a subject may be withdrawn at any time at the discretion of the investigator.

Appendix 11.1. Monitoring

The following laboratory abnormalities require re-testing within 1 week:

- Absolute neutrophil count $<2000/\text{mm}^3$;
- Hemoglobin $<11.0 \text{ g/dL}$;
- Platelet count below $<100,000/\text{mm}^3$;
- Serum creatinine $>$ upper limit of normal (ULN).

Appendix 11.2. Discontinuation

Treatment with PF-04965842 will be discontinued and the subject withdrawn from this study for:

Adverse Events:

- Serious infections, defined as any infection (viral, bacterial, and fungal) requiring parenteral antimicrobial therapy or hospitalization;
- Other serious or severe AEs, after consultation with the Pfizer clinician.

Laboratory Abnormalities:

All the following laboratory abnormalities **require discontinuation** if they are confirmed. Confirmation through re-testing should occur within 1 week:

Laboratory Variable	Laboratory Value
Hematology	
Absolute Neutrophil Count	<1000/mm ³ ; <1.0 x10 ⁹ /L
Hemoglobin	<10.0 g/dL; <6.2 mmol/L; <100 g/L
Platelet count	<75,000/mm ³ ; <75.0x10 ⁹ /L
Lymphocytes	<500/mm ³ ; <0.8x10 ⁹ /L
Chemistry	
AST	>2.5x ULN
ALT	>2.5x ULN
Creatinine (serum)	>1.5x ULN
Total bilirubin ^a	>1.5x ULN

^a Total bilirubin ≥1.5 x ULN; subjects with a history of Gilbert's syndrome may have a direct bilirubin measured and would be eligible for this study provided the direct bilirubin is ≤ ULN

The following vital sign abnormality will **require discontinuation** if it is confirmed. Confirmation through re-testing should occur within 1 week:

- Diastolic: recurrent or persistent (≥24 hrs) or symptomatic increase from baseline, in same posture, by >20 mmHg.

Discontinuation/End of Treatment Monitoring for Adverse Events, Laboratory, and Vital Signs:

Any subject meeting discontinuation criteria must enter into the Follow-up Period with their first follow-up visit occurring 1 week after their last dose, until the event has returned to normal or baseline levels or is deemed clinically stable. The only exception to this is when a subject specifically withdraws consent for any further contact with him or her or persons previously authorized by the subject to provide this information. Additional follow-up visits may occur as needed until any clinically relevant abnormalities or adverse events have resolved, returned to a baseline state, or are deemed clinically stable.

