 - a. A positive QuantiFERON[®]-TB Gold (QFT-G) In-Tube test or positive Mantoux/Purified Protein Derivative (PPD) tuberculin skin test performed at or within the 12 weeks prior to Day 1 is exclusionary; a negative test is required for eligibility. It is recommended that subjects with a history of Bacille Calmette Guérin (BCG) vaccination be tested with the QFT-G test since the Mantoux/PPD tuberculin skin test may be positive due to vaccination. See [Section 7.3.5](#) for requirements for Mantoux/PPD tuberculin skin testing. A QFT-G or Mantoux/PPD tuberculin skin test is not required if the subject has previously received a documented adequate course of therapy for either latent or active TB infection or is currently receiving a documented adequate treatment for latent TB infection;

- b. A history of either untreated or inadequately treated latent or active TB infection;
 - c. If a subject has previously received an adequate course of therapy for either latent (9 months of isoniazid in a locale where rates of primary multi-drug TB resistance are <5% or an acceptable alternative regimen) or active (acceptable multi-drug regimen) TB infection, neither a QFT-G test nor a Mantoux/PPD tuberculin skin test is needed, but a chest radiograph(s) (per local standard/guidelines) must be obtained if not performed within 12 weeks prior to Day 1. To be considered eligible for the study, the radiograph(s) must be negative for active tuberculosis infection as determined by a qualified radiologist. Documentation of adequate treatment for TB and negative chest radiograph(s) results must be obtained prior to Day 1. If the current incidence rates of multi-drug resistant TB infection in the locale are unavailable, an adequate treatment regimen should be defined as the regimen recommended by the health ministry or expert panel in the locale;
 - d. A subject who is currently being treated for active TB infection is to be excluded.
20. **ANY** of the following abnormalities in clinical laboratory tests at screening, as assessed by the study-specific laboratory and confirmed by a single repeat, if deemed necessary:
- Absolute neutrophil count of $<2.5 \times 10^9/L$ ($<2500/mm^3$).
 - Hemoglobin <10.0 g/dL or hematocrit $<30\%$;
 - Platelet count below the lower limit of normal (LLN) at Screening;
 - Absolute lymphocyte count of $<0.5 \times 10^9 /L$ ($<500/mm^3$);

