Clinically significant abnormal findings should be recorded as AEs. Abnormal test results determined to be caused from laboratory error should not be reported as AEs. Clinically significant laboratory findings at the final assessment should be followed to resolution or until determined by the Investigator to be stabilized. Repeat tests may be indicated to establish this. Refer to [Appendix 11](#) for laboratory discontinuation criteria.

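### The lymphocyte stopping rule in Protocol Appendix 11.2 prints two different limits as if they were one: 500/mm³ is 0.5×10⁹/L, not 0.8×10⁹/L

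*Protocol*

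**What the plan says.** Appendix 11 applies to all subjects in the study. Appendix 11.2 opens by stating that "Treatment with PF-04965842 will be discontinued and the subject withdrawn from this study for" the events and values listed under it. The laboratory table there is mandatory once a value is confirmed, and the instruction is that "Confirmation through re-testing should occur within 1 week". The lymphocyte row reads below 500/mm³; below 0.8×10⁹/L.

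Three other places bear on the limit:

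- **Protocol 4.2, Exclusion Criterion 20** excludes subjects with any "of the following abnormalities in clinical laboratory tests at screening, as assessed by the study-specific laboratory and confirmed by a single repeat". The bullet that begins "Absolute lymphocyte count of" gives below 0.5×10⁹/L, with below 500/mm³ in brackets.
- **Protocol 7.5.2** sends the reader to Appendix 11 "for laboratory discontinuation criteria" and gives no limit of its own. The test list there names lymphocytes as percentage and absolute count, without a reporting unit.
- **Appendix 11.1** lists re-test thresholds for neutrophils, haemoglobin, platelets and creatinine, but none for lymphocytes.

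The SAP gives no lymphocyte limit.

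**The concern.** The row is laid out as one limit in two units, but it contains two limits. Someone reading a count in cells/mm³ and someone reading it in 10⁹/L can follow the protocol exactly and reach opposite decisions about the same patient.

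The row is a binding safety rule for an immunomodulating JAK1 inhibitor, and lymphopenia is one of the laboratory abnormalities named in the safety endpoints (Protocol 2.4.2.2). Haematology is drawn at every visit, and about 60 sites will apply the table. If 800/mm³ is intended, a site using 500/mm³ keeps dosing patients who should have stopped. If 500/mm³ is intended, a site using 0.8×10⁹/L withdraws patients who should have continued. In either case no one can say whether a protocol deviation has occurred.

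There is also an indirect route into the efficacy results. Subjects who discontinue from the study before Week 12 count as IGA non-responders (Protocol 9.2.1; SAP 7.1), and the main analyses of the continuous secondary endpoints use observed cases (SAP 8.2.2.2.1).

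**Working it through.** **Conversion.** One litre is 10⁶ mm³, so a count of x/mm³ equals (x ÷ 1000)×10⁹/L.

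**The row as printed.** 500 ÷ 1000 = 0.5, so 500/mm³ = 0.5×10⁹/L. The printed value is 0.8. In the other direction, 0.8 × 1000 = 800, so 0.8×10⁹/L = 800/mm³. The row does not reproduce. The gap is 800 − 500 = 300 cells/mm³, and the ratio is 0.8 ÷ 0.5 = 1.6.

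**The same check on the comparison limits.**

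| Limit | Conventional unit | Converted | Printed | Agrees? |
|---|---|---|---|---|
| Neutrophils, App. 11.2 | 1000/mm³ | 1.0×10⁹/L | 1.0×10⁹/L | yes |
| Platelets, App. 11.2 | 75,000/mm³ | 75.0×10⁹/L | 75.0×10⁹/L | yes |
| Haemoglobin, App. 11.2 | 10.0 g/dL | 100 g/L; 6.206 mmol/L | 100 g/L; 6.2 mmol/L | yes |
| **Lymphocytes, App. 11.2** | **500/mm³** | **0.5×10⁹/L** | **0.8×10⁹/L** | **no** |
| Lymphocytes, Criterion 20 | 500/mm³ | 0.5×10⁹/L | 0.5×10⁹/L | yes |
| Neutrophils, Criterion 20 | 2500/mm³ | 2.5×10⁹/L | 2.5×10⁹/L | yes |

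The haemoglobin line in mmol/L uses an assumed factor of 0.6206 mmol/L per g/dL (10.0 × 0.6206 = 6.206). The documents do not give that factor, and the lymphocyte result does not depend on it.

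**What the row requires for a confirmed count.**

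| Confirmed count | Under 500/mm³ | Under 0.8×10⁹/L |
|---|---|---|
| below 500/mm³ | stop | stop |
| 500 to 799/mm³ | continue | stop |
| 800/mm³ or above | continue | continue |

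**Reading the two entries together does not rescue the row.** If either entry triggers stopping, the limit is 800/mm³ and the 500/mm³ entry is redundant. If both must be met, the limit is 500/mm³ and the 0.8 entry is redundant.

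**Link to eligibility.** Criterion 20 excludes only counts below 0.5×10⁹/L. A subject at 0.5 to just under 0.8×10⁹/L can therefore be eligible at screening and already be below the stopping limit if 0.8×10⁹/L governs.

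**The case against.** The strongest reply is that this is one wrong digit whose intended value can be inferred. For every other parameter shared by Criterion 20 and Appendix 11.2, the stopping limit is no stricter, in any material way, than the entry limit: neutrophils 2500 then 1000/mm³, haemoglobin 10.0 then 10.0 g/dL, platelets the lower limit of normal then 75,000/mm³, AST and ALT above 2 then above 2.5 times the upper limit of normal, creatinine above 1.5 times at both points, and bilirubin at or above 1.5 then above 1.5 times. A lymphocyte limit of 0.5×10⁹/L fits that pattern, and 0.8×10⁹/L would be the only exception.

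The clinical exposure is also bounded. Both halves of the row require stopping below 500/mm³, a re-test is needed first, and the investigator may order extra laboratory tests or withdraw a subject at any time. Sites diverge only if they work from different units or resolve the row differently. Criterion 20 mentions a single study-specific laboratory, although only for screening. The documents also give no lymphocyte data from earlier studies, so an effect on the Week 12 comparison cannot be shown.

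Much of this stands. The pattern makes 0.5×10⁹/L the likelier intention, differing decisions are possible rather than certain, and the efficacy effect is unquantified and may be small. It does not remove the error. An inference from the entry criteria is not a rule that a site can cite, and a stricter on-treatment limit is clinically conceivable. A single laboratory would still have to set its alert at one of two conflicting values.

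**Conclusion.** The row is wrong as written. One mandatory safety threshold appears as two values that differ by 300 cells/mm³ (a factor of 1.6). For confirmed counts of 500 to 799/mm³ the protocol both requires and does not require discontinuation, and neither document says which value prevails. Outside that band the two values give the same decision.

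The conclusion rests on unit conversion alone and needs no assumption about effect size, dropout or sample size. It assumes that the PDF prints 0.8 in that cell. The digit should be checked against the page, although the neighbouring rows all convert, so a misreading is unlikely. The number of patients in the band cannot be derived from the documents. The case for correcting the row is that it is a binding stopping rule, and it does not depend on any demonstrated effect on efficacy.

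**What to change.** The sponsor's clinicians should choose one lymphocyte limit, and both entries in the row should express it:

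- **If 500/mm³ is intended,** change the second entry to 0.5×10⁹/L. The row then matches Exclusion Criterion 20.
- **If 0.8×10⁹/L is intended,** change the first entry to 800/mm³. Then either raise the entry limit in Criterion 20 or explain why a subject may enter while already below the stopping limit.

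Tell all sites and the laboratory which single limit triggers the alert and the confirmatory re-test. The cost is one table cell, by amendment or clarification letter, and one laboratory alert setting. If the lower limit is kept, nothing else in the protocol changes. If the higher limit is chosen, Criterion 20 may need a matching edit. The sample size and the planned analyses are unaffected in either case.
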